8.3 Supportive Analyses of the Primary Outcome Measure

The DSC will perform the following supportive analyses related to the primary objective:

1. Subgroup analyses for age (18 – 25 years, 26 years or greater), sex (Male, Female), race (Black, White, Other), and ethnicity (Hispanic or Latino, Not Hispanic or Latino) will be performed as required by the NIH (NIH, 2016). Four models similar to the main primary outcome analyses will be performed, with the inclusion of an interaction term between induction procedure and the demographic subgroup. Forest plot of odds ratios for each subgroup will be provided.
2. Exclude six participants from the ITT as noted below and repeat the analysis described in Section 8.2.

The study exclusion criteria #10 was updated in the amended protocol v3.0 from the initial criteria that stated: "Admitted to the inpatient detoxification or residential rehabilitation unit more than 3 days prior to consent" and was changed to "Admitted to the inpatient detoxification or residential rehabilitation unit more than 4 calendar days prior to enrollment into to SP or RP". Under protocol v2.0, six participants enrolled in the study who were admitted to inpatient detoxification or residential rehabilitation more than 4 calendar days prior to enrollment. A sensitivity analysis will be conducted for the primary outcome measure that excludes these six participants, per DSMB recommendations on May 5, 2022.

3. For sites that transition from SP to RP a sensitivity analysis will be conducted excluding all participants in the SP in the 8 weeks before crossing over to the RP (i.e., pre-implementation phase) to account for any possible contamination of the SP arm with the RP training.
4. Test for an induction procedure by study month interaction, which, if significant, would indicate differential impact of induction procedure after a longer period of experience.
5. Repeat primary outcome analysis with the inclusion of a covariate for fentanyl use (positive vs. negative) as assessed on the Urine Drug Screen (UDS) form at screening or baseline assessments.
6. Summarize the primary outcome by induction procedure in the subset of participants who initiated buprenorphine.

Other supportive analysis to be performed by LN related to the primary outcome include:

- Repeating analyses in Section 8.2. with the inclusion of potential baseline covariates that were found to be unbalanced between sites or any other baseline covariates that are deemed important predictors of the outcome.
- Prediction in terms of participant level factors that predict success versus failure to initiate XR-NTX adjusting for the following covariates: severity of opioid use disorder based on route of use (IV vs. non-IV) with IV users having a more severe disorder, type of opioid (fentanyl vs. heroin vs. prescription opioid) with fentanyl users being most severe and prescription opioid users least severe, as well as psychiatric and substance use disorder comorbidity will be explored. Site level factors, measured with the implementation measures will also be explored. Although, with 6 sites power for that would be limited. It could be a nested prediction model with patients nested within sites, and site level factors (like staff knowledge and attitudes) in the model.

8.4 Definition of the Secondary Outcome Measures

Key secondary analyses to be conducted by the DSC:

A key secondary objective is to summarize the below outcome to confirm expected characteristics of the RP compared to SP:

1. The time to receipt of first injection of XR-NTX as measured by the number of days from admission to first XR-NTX injection. This will be conducted on the successfully inducted population only. Day of admission is defined as Day 1 (E97ADMDT) as recorded on the ENRC or ENRD forms, and day of first XR-NTX injection (EOIINJDT) is captured on the End of Induction form (EOI). It will be calculated as Date of injection (EOI.EOIINJDT) – Date of admission (ENRC/ENRD.E97ADMDT) +1.

Additional key secondary objectives are to compare the below outcomes of RP versus SP for all enrolled participants (ITT population).

2. Craving for opioids measured by Visual Analog Scales (VAS) as captured daily on the self-reported inpatient opioid craving form (OCI) during induction phase. The OCI form collects intensity of craving both at time of assessment and within the last 24 hours prior to assessment. If either measurement is collected multiple times on the same assessment date, the average measurement will be used for analysis.
3. Opioid withdrawal symptoms as measured by the Subjective Opioid Withdrawal Scale (SOWS) and the Clinical Opiate Withdrawal Scale (COWS). SOWS is captured on the SBW form at baseline and daily during induction phase. COWS is captured on the COW

form starting with day of admission and daily during the induction phase leading to the first XR-NTX injection. Note that during induction, COWS may be measured multiple times per day while SOWS is expected to be assessed only once per day. If multiple SOWS measures are collected on the same assessment date, the average measurement will be used for analysis. If multiple COWS measures are collected on the same assessment, the peak measurement will be used.

4. Retention in the trial to receive at least one XR-NTX injection after the first injection as captured on the XR-NTX Administration (INN) form.
5. Safety, as measured by targeted safety events, overdoses, and serious adverse events related to study medication during the induction phase and during eight weeks of post-induction. Detail on safety outcome analysis is provided in Section 9.0.

Other secondary analyses to be conducted by LN:

Other secondary objectives to be analyzed by the LN are to compare the below outcomes of RP vs. SP for participants who receive the first injection while on the unit (Inducted Population):

- Opioid abstinence, as measured weekly by the Timeline Followback (TLFB) (self-report days using opioids) during the eight weeks of post-induction and proportion of opioid-positive urine tests as captured on the Urine Drug Screen (UDS) form at post-induction 4 week and 8 week visits.
- In addition, craving for opioids, opioid withdrawal symptoms, and safety events will be assessed in the inducted population similar to the key secondary outcomes.

Table 5: Secondary Clinical Outcomes, Outcome Measures and Hypotheses		
Outcome	Outcome Measure	Hypothesis
Time from admission to first XR-NTX injection	Days to first XR-NTX injection	Participants in the RP will receive their first injection significantly faster than those in the SP. Significance/Rationale: The RP decreases the time to the first injection (which has a potential to decrease costs and staff burden).
Opioid craving (VAS) over time	Mean for opioid craving measured by VAS daily during days leading to the first XR-NTX injection, and during post-induction Weeks 1-8	Participants in RP and SP will have comparable intensity of craving during 1) the inpatient treatment period, and 2) during the first week after the first XR-NTX injection. Significance/Rationale: Earlier trial showed comparable craving severity in both procedures (Sullivan et al. , 2017).
Opioid withdrawal (SOWS and COWS) over time	Mean for opioid withdrawal measured by SOWS and COWS score, daily (starting with day of admission) during days leading to the first XR-NTX injection and during post-induction Weeks 1-8	Participants in RP and SP will have comparable severity of opioid withdrawal during: 1) the inpatient treatment period, and 2) during the first four weeks after the first XR-NTX injection. Significance/Rationale: Earlier trial showed comparable withdrawal severity in both procedures (Sullivan et al. , 2017).

Table 5: Secondary Clinical Outcomes, Outcome Measures and Hypotheses

Outcome	Outcome Measure	Hypothesis
Targeted safety events, overdoses and SAEs, related to study medications	Frequency of targeted safety events, overdose episodes and SAEs by relationship to study medication during the induction period and during eight weeks of post-induction treatment	RP and SP will produce equivalent rates of targeted safety events and SAEs during the induction and during the first eight weeks of treatment with XR-NTX. Significance/Rationale: Careful documentation of SAEs, targeted safety events, and overdose episodes, would be considered essential safety data, and important component of a comparative effectiveness trial.
Receive second and third injections (binary: did or did not receive second and third dose of XR-NTX)	Proportion of participants that receive second and third injection of XR-NTX (at 4 weeks and 8 weeks, from first injection)	Participants in RP and SP will have comparable rates of treatment retention. Significance/Rationale: Because there is no difference in tolerability of the first and second XR-NTX injections in both study arms, we do not expect differential treatment dropout.
Use of opioids over time during the 8-week of post-induction treatment while on study medication (Weekly TLFB, confirmed by urine drug screens when available)	Percent of participants positive for opioids using weekly TLFB during eight weeks of post-induction, and urine drug screens at week 4 and 8.	RP and SP will produce comparable levels of opioid use. Significance/Rationale: XR-NTX produces complete blockade of opioid effects, so that during treatment with monthly injections, opioid use can be expected to be minimal and no different between study arms.

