4.1.5 Duration of XR-NTX Treatment

The primary study goal is the success of XR-NTX induction, i.e., receiving the first injection. However, we will continue treatment by offering two additional XR-NTX injections. First, the acceptance of the second and third injections is an important outcome and may be reflective of the tolerability of the first injection and the induction procedure overall. The first three months of XR-NTX treatments is the time when greatest dropout is anticipated (Sullivan *et al.*, 2019) and therefore providing treatment with three consecutive injections is ethically favorable. The post-induction portion of the study will last 8 weeks, until the third XR-NTX injection is given, at which point participants will complete final study assessments and will transition to continuing treatment in the community.

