6.1.4.2 Phase 3 (Post-Induction Phase): Follow-Up Treatment

Following inpatient XR-NTX induction phase, participants will continue with the post-induction treatment for 8 weeks (post-induction Week 1 through Week 8; Days 1 – 55). Most participants will be treated on an outpatient basis during this phase, but some may be in extended residential or therapeutic community programs. Participants that receive first XR-NTX are expected to receive a second injection of XR-NTX towards the end of Week 4 and a third injection towards the end of Week 8 in combination with weekly Medical Management visits. The study will supply the three XR-NTX injections (initial and at Weeks 4 and 8). Study assessment visits occur weekly during this phase, with an End of Study (EOS) visit occurring at Week 8. For participants who request discontinuation of treatment, relapse, and/or become lost to follow up, a +14 day window is permissible to complete the EMT visit.

Patients who fail to initiate XR-NTX while inpatient will also be followed and evaluated at Week 4 and Week 8 to determine what treatment they are receiving (for example, whether they initiated XR-NTX after leaving the unit or if they initiated and remained on another medication (buprenorphine or methadone maintenance)) and whether or not they have relapsed to opioid use.

6.1.4.3 *Phase 4 (Referral Phase) Referral to continuing treatment*

During the last month of study, as part of standard clinical care, arrangements will be made by the clinical team for participants to either continue treatment at the same program or be referred to another program in the community for follow-up care, which should ideally include continuation of XR-NTX. The third XR-NTX injection will be administered as a part of the study in order to objectively assess the retention in treatment 8-weeks after the induction and to assure the continuation of treatment with XR-NTX during the post-study transition period. However, participants will not be followed with study assessments after third injection as at this point, they will be engaged with and followed in the community-based clinical care where they will be assessed medically following standard procedures.

6.1.4.4 *Management of participants who fail to initiate XR-NTX*

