7.2 Secondary Outcome Measure(s)

7.2.1 Table 3: Secondary Clinical Outcomes, Outcome Measures and Hypotheses

Outcome	Outcome Measure	Hypothesis
Time from admission to first XR-NTX injection	Days to first XR-NTX injection	Participants in the RP will receive their first injection significantly faster than those in the SP. Significance/Rationale: The RP decreases the time to the first injection (which has a potential to decrease costs and staff burden).
Opioid Craving (VAS) over time	Mean for opioid craving measured by VAS daily during days leading to the first XR-NTX injection, and during post-induction Weeks 1-8	Participants in RP and SP will have comparable intensity of craving during 1) the inpatient treatment period, and 2) during the first week after the first XR-NTX injection. Significance/Rationale: Earlier trial showed comparable craving severity in both procedures (Sullivan et al. , 2017).
Opioid withdrawal (SOWS and COWS) over time	Mean for opioid withdrawal measured by SOWS and COWS score, daily (starting with day of admission) during days leading to the first XR-NTX injection and during post-induction Weeks 1-8	Participants in RP and SP will have comparable severity of opioid withdrawal during: 1) the inpatient treatment period, and 2) during the first four weeks after the first XR-NTX injection. Significance/Rationale: Earlier trial showed comparable withdrawal severity in both procedures (Sullivan et al. , 2017).
Receive second and third injections (binary: did or did not receive second and third dose of XR-NTX)	Proportion of participants that receive second and third injection of XR-NTX (at 4 weeks and 8 weeks, from first injection)	Participants in RP and SP will have comparable rates of treatment retention. Significance/Rationale: Because there is no difference in tolerability of the first and second XR-NTX injections in both study arms, we do not expect differential treatment dropout.
Targeted safety events, overdoses and SAEs, related to study medications	Frequency of targeted safety events, overdose episodes and SAEs by relationship to study medication during the induction period and during eight weeks of post-induction	RP and SP will produce equivalent rates of targeted safety events and SAEs during the induction and during the first eight weeks of treatment with XR-NTX. Significance/Rationale: Careful documentation of SAEs, targeted safety events, and overdose

Outcome	Outcome Measure	Hypothesis

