Note that participants who fail the induction phase will still be enrolled into the post-induction phase but only assessed at Weeks 4 and 8. Participants who discontinue XR-NTX early (i.e. do not receive both injections) will complete the Early End of Medication Visit and the following assessments will be performed: V97, CMX, MGT, End of Medication (EOM), and End of Medication – Self-Reported (EO2).

Other assessments will be performed as needed: Injection Site Abnormality (INA), Mental Health Follow-Up Assessment (MHA), Study Completion (STC).

In addition to the above assessments, the study will collect data on implementation facilitation outcomes: Organization Level Clinical Implementation (OLC) at the start of each step at all sites, Pre/Post Organizational Readiness to Change Assessment (ORCA) (OR1/OR2) prior to and at the end of RP implementation step at the randomized site, Pre/Post Fidelity to Implementation Checklist (FC1/FC2) at the start and end of RP implementation step at the randomized site. OR1/OR2 collect provider/staff level data whereas OLC and FC1/FC2 collect site level data.

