  random intercept / subject=patid type=ar(1);  
run;
```

where:

- trt - is the variable that defines the induction procedure (RP or SP)
- outcome - is the presence of moderate to severe daily COW score (Yes=1 or No=0)
- step - is 1 through 5
- site - is the site code for the 6 sites.
- day- days since admission to the unit
- patid- participant ID

SAS code example that may be used to analyze continuous SOWS and VAS outcomes:

```
proc mixed data = secondout;  
  class patid site day_cat trt(ref='SP') step (ref='1');  
  model outcome = trt site day step/ solution cl;  
  random intercept / subject = patid;  
  repeated day_cat/ type = AR(1) subject = patid;  
  estimate "trt effect" trt 1 -1;  
run;
```

where:

- trt - is the variable that defines the induction procedure (RP or SP)
- outcome - is either mean SOWS or mean VAS score
- step - is 1 through 5
- site - is the site code for the 6 sites
- day - days since admission to the unit (continuous)
- day_cat- days since admission to the unit (categorical) as required by the repeated statement in the model
- patid- participant ID

Retention in the trial to receive at least one XR-NTX injection after the first inpatient injection as captured on the XR-NTX Administration (INN) form will be analyzed similarly to the primary outcome using a mixed-effects model with logit-link function.

Frequency of targeted safety events, overdose episodes and SAEs by relationship to study medication will be reported. Safety data analysis is provided in detail in Section 9.0.

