Gibson Recovery Center versus ADAPT								
Stony Brook Eastern Long Island Hospital versus ADAPT								

Table 49: Retention in the Study to Receive at Least One XR-NTX Injection after Induction Success

Induction Procedure	Number with Induction Success	At Least One Additional Injection Administered	Results			
			Odds Ratio	95% Lower Confidence Limit	95% Upper Confidence Limit	p-value
Rapid	N (X.x%)	N (X.x%)	X.xx	X.xx	X.xx	0.xxx
Standard						
Total						

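### The SAP models retention as at least one further XR-NTX injection, so the third injection, part of the stated outcome, gets no adjusted comparison there

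*SAP*

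**What the plan says.** Two definitions of retention stand side by side.

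**The endpoint that is modelled.** SAP 8.4, key secondary item 4, is "Retention in the trial to receive at least one XR-NTX injection after the first injection as captured on the XR-NTX Administration (INN) form". SAP 8.5 repeats it as "Retention in the trial to receive at least one XR-NTX injection after the first inpatient injection" and analyses it like the primary outcome, with a logit-link mixed-effects model. The shell for Table 49 has a single outcome column, "At Least One Additional Injection Administered", and the output list in SAP 18.0 names the same endpoint in the inducted population.

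**The endpoint that is stated.** SAP Table 5, also in section 8.4, gives the outcome as "Receive second and third injections (binary: did or did not receive second and third dose of XR-NTX"). Protocol Table 3 gives the measure as "Proportion of participants that receive second and third injection of XR-NTX (at 4 weeks and 8 weeks, from first injection"). SAP 2.1.2 objective 5 and protocol 5.2 objective 5 also name the second and third injections. Protocol 16.3.2 lists the 2nd and 3rd injections among the secondary outcomes and says they will be modelled with mixed-effects logistic regression.

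**The concern.** The trial's own account gives the third injection weight. Protocol 4.1.5 says that "the acceptance of the second and third injections is an important outcome". Protocol 6.1.4.3 says the third injection is "administered as a part of the study in order to objectively assess the retention in treatment 8-weeks after the induction". SAP 2.2.2, when setting out who completes the early end-of-medication visit, refers to "Participants who discontinue XR-NTX early (i.e. do not receive both injections"). Some of those same people would count as retained in Table 49.

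The hypothesis in SAP Table 5 is that retention is comparable in the two procedures. An adjusted analysis that leaves out the third injection could support that hypothesis while the procedures diverge between weeks 4 and 8. The SAP revision history (section 16.0) does not identify the narrower endpoint as a deliberate change.

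**Working it through.** The plan gives no retention rate and no power for retention, so there is no figure to reproduce. The check is a comparison of text, followed by an illustration.

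**1. Where each injection is analysed**

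| Place | Second injection | Third injection |
|---|---|---|
| Protocol 16.3.2 | mixed-effects logistic model | mixed-effects logistic model |
| SAP 8.5, Table 49 | adjusted model, through the at-least-one endpoint | none of its own |
| SAP Table 26 (by site), Table 27 (by procedure) | count and percentage | count and percentage of those who had the second |
| SAP 8.4, lead node's list | not listed | not listed |

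**2. What the modelled endpoint measures.** If injections are numbered in the order received, nobody has a third without a second. Then at least one further injection is the second injection, and receipt of both is the third. The third adds nothing to the modelled endpoint. If they are instead counted by visit, a participant who misses week 4 but is injected at week 8 also counts as at least one, and the equivalence is only approximate.

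**3. Size, for illustration.** From the documents: about 225 participants per procedure (protocol 8.0), with success 0.55 under SP and 0.70 under RP (SAP 12.0). Assumed: s, the proportion of inductees who get a second injection, 0.4 to 0.8; and third-given-second, 0.7 to 0.9, so that d, the proportion with a second but no third, is 0.1 to 0.3.

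- Expected inductees: 225 × 0.55 = 123.75 and 225 × 0.70 = 157.5, total 281.25.
- Counted as retained without both injections: 281.25 × s × d. The low end is 281.25 × 0.4 × 0.1 = 11.25 (4%). The high end is 281.25 × 0.8 × 0.3 = 67.5 (24%).

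**4. Can the two endpoints disagree about the procedures?** Take the same s in both, with third-given-second 0.9 in one and 0.7 in the other:

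| s | At least one, odds ratio | Both injections | Difference | Odds ratio for both |
|---|---|---|---|---|
| 0.4 | 1.00 | 36% v 28% | 8 points | 1.45 |
| 0.6 | 1.00 | 54% v 42% | 12 points | 1.62 |
| 0.8 | 1.00 | 72% v 56% | 16 points | 2.02 |

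For example, at s = 0.4: (0.36/0.64) / (0.28/0.72) = 1.45. The 1.00 follows by construction from equal s.

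**5. Population.** If inductee retention is the same r in both procedures, an all-enrolled comparison still differs by (0.70 − 0.55) × r. That is 6 points at r = 0.4 and 12 at r = 0.8. At r = 0.7 it is 38.5% v 49.0%. This gap comes from induction success alone.

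**The case against.** Several points on the other side stand.

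- **A model does exist.** A reader might infer that the third injection has no specified model at all. That is not so: protocol 16.3.2 names one, and the SAP describes itself as expanding on the protocol. The gap is that the SAP does not carry the model forward.
- **The third injection is not hidden.** A reader might infer that a difference at the third injection would go unseen. Table 27 gives third injections among those with a second, by procedure, so a 90% v 70% split would appear there. What is missing is the comparison adjusted for step and site.
- **The population is not simply wrong.** SAP 8.4 places item 4 under an all-enrolled heading, while SAP 2.1.2 and protocol 5.2 place retention among inductees, as do SAP 18.0 and Table 49. But protocol 16.3.2 asks for post-injection outcomes in both populations, so this is an inconsistent heading. The planned table's population is clear.
- **The label has no inferential effect.** SAP 8.4 makes retention a key outcome and SAP 2.1.2 an other one. SAP 11.0 makes no multiplicity adjustment for secondary outcomes and says the key ones are not meant to be confirmatory.
- **Part of the objective is modelled.** Table 5 can be read as two separate outcomes. Under sequential counting, the existing model covers the first of them.
- **Receipt of both is not a perfect measure.** SAP 2.2.2 is a visit trigger, not a definition of retention. Under protocol 10.5.4 and 10.5.6, injections are at least 21 days apart and study supply ends 77 days after the first. A second injection after day 77 − 21 = 56 therefore leaves no room for a study-supplied third.
- **The rates are assumed.** The 90% v 70% contrast runs against the documents' expectation of no differential dropout. It shows that the endpoints can disagree, not that they will.

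None of this explains why SAP 8.5 and Table 5 use different endpoints.

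**Conclusion.** The mismatch holds. The SAP's only adjusted retention analysis uses at least one further injection, while the objective and outcome tables in both documents, and the protocol's analysis section, use the second and third. With sequential counting, the adjusted analysis equals receipt of the second injection and cannot detect a difference arising at the third.

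The consequence is limited. This is one non-confirmatory secondary outcome, third-injection counts are still reported by procedure, and the primary analysis and its power do not change. The sizes (4-24% of inductees classified differently; hidden differences of 8 to 16 points) rest on planning induction rates and assumed injection rates. It should be corrected because the change is small and restores what the protocol already specifies.

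**What to change.** In SAP 8.4 item 4, 8.5, 18.0 and Table 49, model receipt of the second injection and receipt of the third, or both jointly, and state which reading of Table 5 is meant. State also whether injections are counted in sequence or by visit. Use the inducted population as SAP 3.1.5 defines it (first injection on the unit) and the model already planned: procedure and step as fixed effects, with a random intercept for site. At least one further injection may stay as a supplementary endpoint.

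Editorially, reconcile the all-enrolled heading and the key label in 8.4 with SAP 2.1.2, SAP 18.0 and Table 49.

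If the all-enrolled analysis in protocol 16.3.2 is kept, the sponsor should define how induction failures' injections are counted. Protocol 10.5.5 lets these participants receive study-supplied XR-NTX, and protocol 12.2.9 records it only on the M97 form. A rule based on the INN form alone would code them as not retained. The report should also note that this analysis partly repeats the primary outcome.

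The cost is SAP wording and a revised Table 49. For inductees, the second and third injections are already collected on the INN form (SAP 7.0).
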